# "NON-INTERVENTIONAL (NI) STUDY PROTOCOL"

# **Study information**

Title	A retrospective analysis of Inotuzumab ozogamicin
	(InO) usage in adult patients with
	relapsed/refractory (R/R) B-cell Acute
	Lymphoblastic leukemia (ALL)
Study Design	A multicentric retrospective cohort analysis of adult
	R/R B-cell ALL patients treated with Inotuzumab
	ozogamicin at tertiary care institutions.
Protocol number	B1931043
Protocol version identifier	Version 1.0
Date	14 November 2022
Active substance	Antineoplastic agents, other Antineoplastic agent,
	monoclonal antibodies, ATC code: L01XC26
	Inotuzumab Ozogamicin
Medicinal product	Inotuzumab Ozogamicin
Research question and	We aim to carry out a multicentric retrospective
objectives	cohort analysis with data of approximately 55
	patients treated with Inotuzumab ozogamicin
	monotherapy to provide clinical outcomes in real-
	world clinical practice in India.
Author	PPD

PPD

This document contains confidential information belonging to Pfizer. Except as otherwise agreed to in writing, by accepting or reviewing this document, you agree to hold this information in confidence and not copy or disclose it to others (except where required by applicable law) or use it for unauthorized purposes. In the event of any actual or suspected breach of this obligation, Pfizer must be promptly notified.

# 2. LIST OF ABBREVIATIONS

Abbreviation	Definition	
ADC	antibody-drug conjugate	
AE	adverse event	
AEM	adverse event monitoring	
allo-HCT	allogeneic hematopoietic stem cell transplantation	
CNS	central nervous system	
CR	complete remission	
Cri	complete remission with incomplete hematologic	
	recovery	
CRF	case report form	
DOR	duration of remission	
FDA	Food and Drug Administration	
GCP	Good Clinical Practice	
нѕст	haematopoietic stem cell transplantation	
IEC	Independent Ethics Committee	
ІСМЈЕ	International Committee of Medical Journal Editors	
InO	Inotuzumab ozogamicin	
IQR	interquartile range	
IRB	Institutional Review Board	
MoAb	monoclonal antibody	
MRD	minimal residual disease	
NIS	non-interventional study	
OS	overall survival	

PFIZER CONFIDENTIAL

CT24-WI-GL02-RF02 4.0 Non-Interventional Study Protocol Template For Secondary Data Collection Study 01-Jun-2022 Page 5 of 24

Ph	Philadelphia chromosome	
R/R B cell ALL	Relapsed/Refractory/ B Cell Acute lymphoblastic leukemia	
RFS	relapse free survival	
SD	standard deviation	
SDV	source data verification	
SOS	sinusoidal obstruction syndrome	
ТКІ	tyrosine kinase inhibitor	
TRAE	treatment-related adverse event	
US	United States	
VOD	veno-occlusive disease	
YRR	your reporting responsibilities	

# **3. KEY DEFINITIONS**

Index date: The date of initiation of the first cycle of InO.

**Baseline period**: Period from 6 months before index date to the index date. The closest observation recorded during the baseline period and closest to index date will be used as baseline data (when more than one observations are available).

**CR/CRi rate**: Number of patients who achieve complete remission/complete remission with incomplete hematologic recovery (CR/Cri) divided by the total number of patients completing treatment with InO (defined as patients with a recorded date of discontinuation of InO).

**Complete remission (CR)**: is defined as 5% bone marrow blasts, no evidence of disease in the bone marrow, and recovery of peripheral blood count (platelet count of >  $100 \times 109/L$  and absolute neutrophil count of >  $1 \times 109/L$ ).

**CR with incomplete count recovery (CRi)**: is defined as 5% bone marrow blasts and no evidence of disease in the bone marrow, but with incomplete recovery of peripheral blood count. Minimal residual disease (MRD) will be assessed at each participating institution by multicolor flow cytometry.

**MRD negativity r**ate: Proportion of patients in whom minimal residual disease (MRD)-negative status is observed, among patients in whom MRD negativity status has been assessed, at any time until the end of treatment with InO (defined as the date of recorded discontinuation of InO). OS: Time from index date to death.

**RFS:** Time from index date to the earliest date of the following events: death, progressive disease (including objective progression, relapse from CR/CRi, treatment discontinuation due to global deterioration of health status), or the start of new induction therapy or posttherapy haematopoietic stem cell transplantation (HSCT) without achieving CR/CRi.

**EMD**: Extramedullary disease is the presence of leukemic cell aggregates in the form of solid tumor outside that of bone marrow.i

LBL: lymphoblastic lymphoma, is a clonal hematopoietic stem cell disorder of B or T cell originii

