### 9.6.2. Reporting and Publication of Data:

Insignia will prepare a Study report within 2 months after the completion of the last patient. If a report of the study is published, the contribution of participating doctors will be duly acknowledged.

Insignia is obliged to analyze and report all study data as described in the protocol.

In accordance with the Declaration of Helsinki, both authors and publishers have ethical obligations. In publication of the results of the study, the authors are obliged to preserve the accuracy of the results. Negative as well as positive results should be published or otherwise publicly available. Insignia endeavors to publish the results of study and is committed to ensure that the data are reported in a responsible and coherent manner.

Insignia seeks to ensure that publications in biomedical journals follow the guidelines established by the International Committee of Medical Journal Editors (ICMJE) and published in its Uniform Requirements of Manuscripts Submitted to Biomedical Journals.

Insignia is committed to ensuring that authorship for all publications should comply with the criteria defined by the ICMJE. These state that: "Each author should have participated sufficiently in the work to take public responsibility for the content."

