# 4.1 FULL ANALYSIS SET

The restrospective available record of all Relapsed/Refractory B Cell Acute lymphoblastic leukemia adult patients satisfying specified inclusion and exclusion criteria will be the full analysis set.

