# 4.3 OTHER ANALYSIS SET

• No other data set will be used for this study

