# 5.1 EFFICACY/EFFECTIVENESS ENDPOINT(S)

The primary outcomes of interest are CR/CRi achieved or not following InO treatment which will be measured by binary response and duration of remission which will be measured by time to achieve CR/Cri from InO therapy starts. Other secondary outcomes will be measured by binary response mostly, but time to event for dealth and relapse will be measured by time from starting of the therapy to the event of interest. The longest time from initiation of InO to date of data extracted will be considered as study period. The number of salvage therapies received prior to the InO therapy initiation will be classified into 0, 1 and >1.

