# 6 HANDLING OF MISSING VALUES

Owing to the descriptive nature of the study, analysis will be on available data only. No imputation of missing data will be implemented.

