# 7 STATISTICAL METHODOLOGY AND STATISTICAL ANALYSES

# 7.1 STATISTICAL METHODS

Means, medians, and standard deviations will be provided for continuous variables when performing descriptive analysis of continuous data. Numbers and percentages will be provided for dichotomous and polychotomous variables when performing descriptive analysis of categorical data. The proportion of CR/CRi achieved will be compared across the number of salvage therapies prior to InO initiation with respective 95% confidence interval. Kaplan-Meier survival curve will be drawn for longest time from initiation of InO to date of data extracted. Similarly survival curve will be drawn for relaspse free survival. Median survival or restricted mean survival time will be reported across the number of salvage therapies.

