# 7.2 STATISTICAL ANALYSES

The distribution demographics variables like age and sex will be summarized by mean  $\pm$ SD and frequency (%) respectively. The prevalence of complete remission or complete remission with incomplete hematological recovery following treatment with InO will be reported with 95% confidence interval. Further these prevalence will be estimated for the

number of salvage therapies  $(0, 1, \ge 2)$  received before InO initiation.6 months or 12 months restricted mean remission free time will be estimated with 95% CI for both complete remission or complete remission with incomplete hematological recovery. The Kaplan-Meier curves of remission free survival will be drawn if a sufficient representation observed across the number of salvage therapies  $(0, 1, \ge 2)$  received before InO initiation. The restricted mean remission free time with 95% CI will be estimated for categories of number of salvage therapies. Restricted mean/median survival time will also be estimated with 95% CI. The Kaplan-Meier overall survival curve will also be drawn.

Other secondary endpoints like MRD negativity following initiation of InO or dosage pattern, concomitant medications, cause of death , occurrence of Grade 3/4 treatment-related adverse events in lung/cardiac/kidney/liver etc. following InO initiation and CR/CRi in EMD/LBL will also summarized by frequency and percentage and dration of response(DOR), no of patients who proceeded to transplant, total during study treatment and post HSCT will be summarized my median and interquartile range. restricted relapse-free-survival time will also be estimated with 95% CI if data permits for all patients and patients with or without follow-up HSCT.

Due to non-probability sampling technique, the extrapolation of the results will be restricted to the population that matches with sample characteristics only. Magnitude of the measure of any characteristics will be prioritised over statistical interpretation. However, interpretation of the result will be in a qualitative sense even though the related feature is compared numerically owing to descriptive nature of the study.

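### The primary CR/CRi rate is divided by patients with a recorded InO stop date, which eligibility does not require, and the numerator is not tied to the same patients

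*Protocol*

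**What the plan says.** Protocol section 3 defines the CR/CRi rate as the number of patients who achieve CR or CRi "divided by the total number of patients completing treatment with InO (defined as patients with a recorded date of discontinuation of InO"). Protocol 9.6.2 then binds the vendor to the protocol: "Insignia is obliged to analyze and report all study data as described in the protocol".

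The eligibility criteria (Protocol 9.1.1 and 9.1.2, repeated in SAP 4.1) require at least one completed cycle of InO. They do not ask for a stop date.

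The SAP's full analysis set is the records of all patients "satisfying specified inclusion and exclusion criteria will be the full analysis set", and SAP 4.3 adds: "No other data set will be used for this study". For the primary outcome:

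- SAP 5.1 describes "CR/CRi achieved or not following InO treatment which will be measured by binary response".
- SAP 7.1 says: "The proportion of CR/CRi achieved will be compared across the number of salvage therapies prior to InO initiation with respective 95% confidence interval".
- SAP 7.2 says: "The prevalence of complete remission or complete remission with incomplete hematological recovery following treatment with InO will be reported with 95% confidence interval".

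None of these names a denominator, and SAP A1.2, reserved for further endpoint definitions, contains nothing. On missing values, SAP 6 says that "analysis will be on available data only", without imputation.

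**The concern.** CR/CRi by number of prior salvage therapies (0, 1, ≥2) is the primary endpoint. Its written definition has three weaknesses.

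- The denominator is set by something that happens after the index date and must also have been written down. Protocol 9.7 expects patients to be lost to follow-up because of adverse events or lack of efficacy. If such patients lack a stop date, likely treatment failures leave the denominator.
- The numerator is not drawn from the denominator. The MRD-negativity rate in the same section is properly nested, being a proportion among patients assessed for MRD. The CR/CRi rate lacks that link, and a binomial confidence interval presupposes it.
- The SAP's single analysis set points to a different denominator, all eligible patients, and its available-data rule could suggest a third, patients with a response assessment. Two analysts could report different primary rates from the same records.

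**Working it through.** The plan states no target rate or precision, so there is no figure to reproduce. The check is how far the rate moves under each reading.

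**Inputs**

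- n = 32 (Protocol Administrative Change Letter, item 4). The SAP still says about 55 (Study population), so 55 is shown too.
- k = responders. 26 of 32 and 45 of 55 are the counts nearest the 81% overall response rate for InO quoted in Protocol section 7; 20 of 32 is a lower scenario. All are illustrations, not design assumptions of this study.
- m = eligible patients without a recorded stop date. Not given; 0, 1 and 2 are assumed.
- r = responders among those m patients, from 0 to m.

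**Formulas**

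- Full analysis set: k/n.
- Protocol section 3 read literally: k/(n − m). This is never below k/n, and it exceeds 1 exactly when m > n − k.
- Numerator limited to the same dated patients: (k − r)/(n − m). This lies below k/n when r/m > k/n and above it when r/m < k/n, so the direction is not fixed.

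**Whole cohort, literal reading**

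| k/n | m = 0 | m = 1 | m = 2 |
|---|---|---|---|
| 26/32 | 81.3% | 26/31 = 83.9% | 26/30 = 86.7% |
| 20/32 | 62.5% | 20/31 = 64.5% | 20/30 = 66.7% |
| 45/55 | 81.8% | 45/54 = 83.3% | 45/53 = 84.9% |

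The shifts run from 1.5 points (45/55, one undated) to 5.4 points (26/32, two undated). The exact (Clopper-Pearson) 95% interval for 26/32 is 63.6% to 92.8%.

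**Whole cohort, numerator limited to dated patients (k = 26, n = 32)**

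- One undated: 25/31 = 80.6% if that patient responded, 26/31 = 83.9% if not.
- Two undated: 24/30 = 80.0% if both responded, 26/30 = 86.7% if neither did.

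**Salvage strata**

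Stratum sizes are not given. Eleven, about a third of 32, is assumed, with 9 responders. One undated patient moves 9/11 = 81.8% to 9/10 = 90.0% on the literal reading.

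**When the literal ratio passes 100%**

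- Whole cohort with k = 26: m must exceed 32 − 26 = 6, so at least 7 of 32 (21.9%) undated. If stop dates were missing independently, the chance of this is 0.1% at 5% missing and 3.6% at 10% missing (both rates assumed).
- Stratum of 11 with 9 responders: m must exceed 2. Three undated (27%) give 9/8 = 112.5%.

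**How many undated patients are plausible**

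Taking 28 February 2022 as the last eligible start and 13 February 2023 as the revised start of data collection, at least 350 days (11.5 months) separate the two. Few patients should still be on treatment without a stop date.

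**The case against.** The strongest reply is that the defect may never show. At least 350 days separate the last start from data collection, CRF blocks may not be left empty (Protocol 9.4.1) and sites are contacted about missing items (Protocol 9.6.1). This stands as an argument about size. It does not guarantee complete dates: the CRF rules allow a not-applicable entry, Protocol 9.7 concedes that records may not cover every data point, and a query cannot recover a date that was never recorded.

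A second reply is that Protocol 9.1.2 and SAP 5 speak of a cohort that has had the full treatment, with the data needed for the endpoints available. That could bring the full analysis set and the stop-date group together. But full treatment is undefined, is not a listed criterion and mentions no stop date.

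A third is that the SAP's words, proportion and prevalence with a confidence interval, imply a nested numerator. Most analysts would read it so. That removes values above 100% but not the selection of patients by whether a date was recorded.

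A reader might infer that the rate will exceed 100%, or is bound to be inflated. The documents support neither. The first needs the literal reading and many undated patients; the second holds only on the literal reading. A reader might also infer two competing written rules. There is one, in Protocol section 3; the full analysis set is only an implied alternative.

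**Conclusion.** The definition is wrong as written and should be fixed. It makes the primary rate depend on a post-index, record-dependent condition that eligibility does not impose, leaves the numerator outside that condition, and differs from the denominator that the SAP's only analysis set implies.

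The size is uncertain. With one or two undated patients (assumed), the whole-cohort rate moves by 1.5 to 5.4 points on the literal reading, small against an interval of roughly 64% to 93% at 26/32. Small salvage strata are more exposed: about 8 points for one undated patient in 11. Values above 100% are an extreme case, mainly conceivable in those strata. If every stop date is recorded, the stop-date and full analysis set rates are the same. Confidence is high on the text and arithmetic, and low on whether the reported result would change.

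**What to change.** In Protocol section 3 and SAP 5.1 and 7.2, define the rate as: full analysis set patients with documented CR/CRi divided by all full analysis set patients, overall and by number of prior salvage therapies (0, 1, ≥2), with the numerator drawn from the denominator.

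- Report the number without a response assessment in each stratum. They stay in the denominator as patients without documented CR/CRi. State in SAP 6 that this is an exception to the available-data rule, and show the available-data rate alongside.
- Keep any stop-date version only as a labelled sensitivity analysis, with numerator and denominator from the same patients.

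The cost is wording in two documents, with IRB/IEC approval of the protocol change (Protocol 10.2). No new data are needed. The headline rate may be less favourable, and it will understate response if some unassessed patients did respond; the available-data rate alongside lets the reader judge that.

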#### 9.1.1. Inclusion criteria

- Patients must meet all of the following inclusion criteria to be eligible for inclusion in the study:
- Patient Population -
- Patients aged ≥18 years old at the initiation of InO treatment
- Patients with relapsed/refractory B-cell ALL
- Patients who initiated InO monotherapy between Feb'2017 and Feb'2022 and are CD22 positive
- Ph+ patients who have failed treatment with at least 1 TKI

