#### 9.1.4. Secondary endpoints

- MRD Negativity following initiation of Ino
- Number of cycles of InO needed to attain CR/CRi
- DOR
- Dosage pattern: InO doses, dose modifications, and the number of cycles of treatment;
- Concomitant medications
- Rate of transplant (No of patients who proceeded to transplant)
- Survival rate at 6 months & 12 months (transplanted patients & non transplanted patients, in both who achieved CR/CRi and MRD negativity)
- Cause of death
- Relapse-free-survival; in all patients and patients with or without follow-up HSCT.
- Rate of VOD (Total, during study treatment and post HSCT, if any patient underwent HSCT) in transplanted & non transplanted patients.
- Occurrence of Grade 3/4 treatment-related adverse events in lung/cardiac/kidney/liver etc following InO initiation; in all patients and patients with or without follow-up HSCT & hematological toxicities
- CR/CRi in EMD/LBL

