# 7.2.2 Analyses of endpoint

The following tables and figures will be generated for the analysis of endpoints.

- 1. The distribution of demographics characteristics (mean ±SD for age and frequency and percentage for sex)
- 2. MRD negativity following initiation of InO (frequency and percentage)
- 3. Dosage pattern (frequency and percentage)
- 4. Cause of death (frequency and percentage)
- 5. Occurrence of Grade 3/4 treatment-related adverse events in lung/cardiac/kidney/liver etcfollowing InO initiation (frequency and percentage)
- 6. CR/CRi in EMD/LBL (frequency and percentage)
- 7. Duration of response (DOR) (Median and Interquartile Range (IQR))
- 8. No of patients who proceeded to transplant (Median and IQR)
- 9. Total during study treatment and post HSCT (Median and IQR)
- 10. Restricted remission free time with 95% confidence interval for both complete remission and complete remission with incomplete hematological recovery.

- 11. Restricted remission free time with 95% confidence interval for both complete remission and complete remission with incomplete hematological recovery stratified by the number of salvage therapies  $(0, 1, \ge 2)$  received before InO initiation
- 12. Restricted mean overall survival time with 95% CI.
- 13. Restricted relapse-free-survival with 95% CI for all patients and patients with or without follow-up HSCT.

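### CR and CRi are defined by marrow and blood counts alone, so the planned CR/CRi rate in EMD/LBL does not measure response at the disease site

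*Protocol*

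**What the plan says.** Protocol section 3 (Key Definitions) holds the only response definitions in either document. CR needs marrow blasts at the 5% limit, "no evidence of disease in the bone marrow, and recovery of peripheral blood count", with platelet and neutrophil thresholds. CRi needs the same marrow state: "no evidence of disease in the bone marrow, but with incomplete recovery of peripheral blood count". Neither refers to examination, imaging or any site outside the marrow.

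The same section defines EMD as the "presence of leukemic cell aggregates in the form of solid tumor outside that of bone marrow", and LBL as follows: "lymphoblastic lymphoma, is a clonal hematopoietic stem cell disorder of B or T cell origin". It gives no response criteria for either.

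Protocol section 9.1.4 lists "CR/CRi in EMD/LBL" as a secondary endpoint. The SAP repeats it among its secondary endpoints (section 5) and gives it a table of counts and percentages (item 6 in sections 7.2.2 and 8). SAP A1.2, the place for further endpoint definitions, reads None, and Appendix 1 on data derivation is marked not applicable. The administrative change letter does not touch the definitions.

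The primary endpoint (protocol 9.1.3, SAP 5.1) is CR/CRi, scored as achieved or not after InO. EMD/LBL patients are not set apart from it.

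**The concern.** The response rule examines the marrow and the blood, while the disease that this endpoint concerns lies, by the protocol's own definition, outside the marrow. A patient can have marrow disease that clears while the masses stay, and on the written rule that patient is in CR or CRi.

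Two results are at stake. The EMD/LBL rate would report marrow status under the name of response in EMD/LBL. The primary CR/CRi rate would include the same patients as responders, as would the endpoints that use the same status: cycles needed to reach CR/CRi, duration of remission, and survival among patients who achieved CR/CRi.

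**Working it through.** There is no figure in the plan to reproduce. The study size rests on availability: about 55 in the protocol body and SAP, changed to 32 by the administrative change letter. The check is therefore a reading of the rule, followed by an illustration on assumed counts.

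**Step 1: apply the rule.** Take an EMD/LBL patient with a clear marrow after InO and a mass that persists.
- Blasts within the limit: met.
- No disease in the marrow: met.
- Counts: recovered gives CR; not recovered gives CRi.
- Mass: not consulted by any criterion.

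The patient meets CR or CRi whatever the state of the mass.

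**Step 2: look for a correction elsewhere.** SAP A1.2 and Appendix 1 are empty. The only wording that could reach a mass is objective progression, in the RFS definition. That is an RFS event and not a condition of CR/CRi, and a stable mass would not trigger it.

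**Step 3: effect on RFS.** RFS runs from the index date, so its start does not move. One of its events is new induction therapy, or HSCT after therapy, without CR/CRi having been achieved. If a patient is labelled CR/CRi on the marrow alone, that event is not counted, and RFS runs on to the next qualifying event or to censoring. This is the only effect on RFS.

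**Step 4: size, on assumed counts.** The documents do not say how many EMD/LBL patients there are. For one patient scored as a remission on the marrow alone, the shift in a rate is 1/N.
- Primary rate, N = 32: 1/32 = 3.1 points. At N = 55 it would be 1/55 = 1.8 points. Section 3 divides by patients with a recorded InO discontinuation date, so the denominator may be below 32 and the shift somewhat larger.
- EMD/LBL rate, with 2, 3 or 6 patients in the group (about 5%, 10% or 20% of 32): 1/2 = 50, 1/3 = 33 and 1/6 = 17 points.

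The next table shows the primary rate at N = 32 with exact (Clopper-Pearson) 95% intervals. The responder counts of 21 and 16 are assumptions. They are the patients who would be responders if extramedullary clearance were also required.

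| Extra patients scored on marrow alone | Starting from 21/32 | Starting from 16/32 |
|---|---|---|
| 0 | 65.6% (46.8–81.4) | 50.0% (31.9–68.1) |
| 1 | 68.8% (50.0–83.9) | 53.1% (34.7–70.9) |
| 3 | 75.0% (56.6–88.5) | 59.4% (40.6–76.3) |
| 6 | 84.4% (67.2–94.7) | 68.8% (50.0–83.9) |

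One such patient changes the primary rate little against the width of its interval. Six would change it materially.

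**The case against.** The strongest reply is that charts are abstracted by the treating team (protocol 9.1), and the CRF must agree with the chart (9.4.2). A clinician may have recorded remission only after imaging showed that the masses had gone. This stands in part. The documents do not say whether charted remissions are taken over or re-derived from section 3, so it cannot be claimed that sites will record false remissions. But if sites use their own criteria, scoring can differ between them, and source data verification has no written extramedullary rule to check against.

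A second reply concerns a marrow already clear at baseline. A reader might infer that such a patient is automatically a responder, or even that the EMD/LBL rate must be 100% whatever the drug does. The documents do not support that. Section 3 counts patients who achieve CR/CRi, and the endpoint is remission following treatment, which naturally implies a change. The 100% figure would need every EMD/LBL patient to enter with a clear marrow and still be counted. Eligibility is "Patients with relapsed/refractory B-cell ALL"; no minimum blast level is set, but LBL is not named, and whether isolated LBL qualifies is not stated. The lowest burden band, under 50%, is an analysis subgroup and shows nothing about who enters. What remains is that no rule says how a patient with a clear marrow at baseline is to be scored.

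A reader might also infer that RFS begins from a false remission. It does not, because it begins at the index date, and growing masses can count as objective progression.

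Finally, the study is descriptive, with no hypothesis or decision rule, and SAP 7.2 asks for qualitative interpretation. This bears on severity. It does not make a rate meaningful when its criterion leaves out the disease site.

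**Conclusion.** The point holds. The written CR and CRi criteria do not cover extramedullary sites, no other response rule exists, and CR/CRi in EMD/LBL is a planned endpoint. As written, that rate does not measure response at the disease site, and any patient with a cleared marrow and persisting masses also enters the primary rate as a responder.

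The size is unknown. The number of such patients is not given and may be small or zero. On assumed counts, each one is worth about 3 points in the primary rate (denominator 32) and 17 to 50 points in the EMD/LBL rate (group of 2 to 6). The effect on RFS is confined to the one event described above.

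This should be fixed. The endpoint directly affected is secondary, and the spill-over into the primary rate depends on patients whose number the documents do not give.

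**What to change.** 1. Add to both the CR and the CRi definition in protocol section 3, and repeat in SAP A1.2: *and no evidence of extramedullary disease, as documented by examination or imaging already in the record*.
2. Abstract from existing charts the marrow and extramedullary status at baseline, and the extramedullary status at response. The CRF is not part of the documents, so some of these fields may already exist.
3. Report EMD/LBL patients with no documented extramedullary reassessment as a separate not-evaluable count, and add a sensitivity analysis that counts them as not CR/CRi. Counting them as non-responders in the main analysis would sit badly with SAP section 6, which analyses available data without imputation, and could bias the rate downward because incomplete records are expected (protocol 9.7).
4. State that an EMD/LBL patient whose marrow was already clear at baseline can achieve CR/CRi only through documented extramedullary resolution.

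The cost is a few sentences in two documents, a little more abstraction and possibly a slightly lower CR/CRi rate. No new procedure is needed, and patient care is not affected.
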